7.3 During intervention

- Haemoglobin concentration (all measurements with date and time) Hb concentrations used can be a formal laboratory result, or where local practice is for clinical decisions to be made using the Hb concentration from a blood gas result this can be used in the trial. Laboratory results are preferable.
- red blood cell transfusions (date; number of units)
- new infections (defined as clinically suspected or proven infection treated with a course of antibiotics)
- any MACE (non-fatal stroke, non-fatal myocardial infarction, cardiovascular death); Definition of stroke and myocardial infarction is 'confirmation by the clinical team that patient has experienced a stroke or myocardial infarction'
- transfusion related adverse events.

7.4 Follow-up at 30 days, 90 days, 180 days and 5 years

Measurements as per table 1

7.5 Source Data Documentation

Source data will be the medical record at each site or the study specific questionnaires and tests according to the data variable.

7.6 Case Report Forms

Case Report Forms (CRFs) will be provided to sites, reflecting the study specific database data requirements. Site staff can complete the paper CRF (pCRF) and then enter this data on to the secure study specific database via individual logins. Alternatively, site teams can decide to enter data directly onto the study database from the source. The site specific Source Data Plan(SDP) will identify the approach to be taken and what is considered source for relevant study data..

All case report forms will be reviewed and approved by the ACCORD Monitor prior to use (see ACCORD SOP CR013 CRF Design and Implementation).

7.7 Trial database

Edinburgh Clinical Trials Unit (ECTU) will provide and maintain a secure web based database compliant to Sponsor SOPs using the REDCAP system. Data will be entered by those staff delegated to do so on the delegation log held at site.

Routine data quality checks will be carried out by ECTU in accordance with their practice.

At the end of the trial, electronic data will be archived by ECTU.

8 DATA MANAGEMENT

8.1.1 Personal Data

The following personal data will be collected as part of the research:

Patients:

Name, CHI number or other unique numeric identifiers, date of birth

Personal data will be stored by the research team in a secure locked environment. Only approved delegated members of the local research team or wider study team will have access to personal data.

Personal data will be stored for 5 years after the end of the trial.

SWAT participants (research staff):

For the SWAT participants we will collect the minimum level of personal detail. All secure data will be stored in an encrypted study folder in DataStore (The University of Edinburgh's networked storage facility). DataStore is encrypted with Veracrypt and accessed via password protected desktops or encrypted laptop. Once the data collection is complete and transcripts checked, interview recordings will be deleted.

Interviews will be recorded on a recording device with 256-bit AES encryption or an equivalent algorithm. Also, the device will have a PIN or password lock to ensure restricted access.

8.1.2 Transfer of Data

Data collected or generated by the study (including personal data) will not be transferred to any external individuals or organisations outside of the Sponsoring organisation unless part of the trial.

Specifically, the analysis of blood samples for erythrogenesis markers will be undertaken in Oxford, and samples will be transferred for analysis (co-investigators [name], [name], [name]). Samples should be stored at sites as per the sampling SOP until arrangements are made to transfer them for analysis.

8.1.3 Data Controller

The University of Edinburgh and NHS Lothian are joint data controllers.

8.1.4 Data Breaches

Any data breaches will be reported to the University of Edinburgh and NHS Lothian Data Protection Officers who will onward report to the relevant authority according to the appropriate timelines if required.

9 STATISTICS AND DATA ANALYSIS

9.1 SAMPLE SIZE CALCULATION

Based on our previous research^{2 18} we estimated mean PCS SF-36 at 90 days will be significantly reduced at 35-40 (normal population average value 50), with standard deviation (SD) of 10-15 points. We defined a minimum clinically important difference as 5 points of the PCS element of the SF-36 at 90 days (smaller differences are of unlikely importance to patients)⁴¹. This represents an effect size of 0.42. Assuming the mean (SD) PCS will be 38 (SD 12) with restrictive (usual) care, to detect an improvement from RBC transfusion to a mean PCS of 43 at 90% power (two-sided P value 0.05) would require 244 patients.

In this population there is a risk of loss to follow-up (other than death), which in most previous trials has been between 10% and 30%. We originally proposed to inflate the sample size allowing for a 20% loss to follow-up at 90 days. This required a sample size of 305 (randomised 1:1 between the two groups). Adjusting for pre-specified baseline covariates is expected to further increase study power and/or protect against extra variability.

In May 2024, follow-up completion for the primary outcome was 75% despite active attempts to maximise this. As part of the strategy to ensure internal validity and adequate study power it was agreed to increase the sample size to ensure complete follow-up for at least 244 surviving patients. Rates of deaths during follow-up were

12/182 (7%). A conservative approach was agreed, assuming loss to follow-up might be as high as 30%. This required an inflation in sample size from 305 to 346 patients to ensure at least 90% power for a difference in the SF-36 PCS of 5 points.

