4 STUDY POPULATION

4.1 NUMBER OF PARTICIPANTS

The total sample size is 346, allocated 1:1 between the two randomised groups.

We anticipate recruitment will take place in 20-25 sites UK-wide, but more sites will be included according to interest, resources, and recruitment rates. Sites outside the UK will be considered if feasible.

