9.2 PROPOSED ANALYSES

All details of the statistical approaches will be specified in a comprehensive Statistical Analysis Plan (SAP), authored by the study statistician and approved by the independent oversight committees (TSC and DMC).

General considerations: will use the Intention-To-Treat (ITT) principle for all outcomes, to estimate treatment effectiveness. However, safety data will be analysed according to treatment actually received instead of treatment allocated.

Principle analysis of PCS SF-36 score: The primary endpoint (change from baseline PCS SF-36 score) at 90 days post randomisation will be compared between randomised groups using a mixed effects linear model, with site as a random effect, and adjustment for any strongly prognostic baseline parameters (which may include age, comorbidity score, pre-ICU recalled HRQoL, length of ICU stay, ICU mobility scale, and baseline inflammation (assessed by CRP concentration)). The expectation is that around 20-30% of those randomised will have some missing data on the primary endpoint. We will address these missing data using an appropriate model for the missing data-generating mechanisms and conduct sensitivity type analyses to investigate the robustness of the findings to the assumptions behind this model.

In addition to the full ITT approach for the primary endpoint, (i.e. the real-world effect of the intervention amongst all those offered the intervention) we will also estimate the treatment efficacy (the idealised effect achieved by those fully compliant with their randomised treatment and all aspects of the protocol).

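### Section 9.1: 346 randomised does not yield 244 surviving completers at 30% loss, and the text does not say whether that 30% includes deaths

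*Protocol*

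**What the plan says.** All the inputs are in protocol section 9.1, with the total repeated in section 4.1.

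- Effect: "We defined a minimum clinically important difference as 5 points of the PCS element of the SF-36 at 90 days".
- Control arm: "Assuming the mean (SD) PCS will be 38 (SD 12) with restrictive (usual) care".
- Base size: an improvement to a "mean PCS of 43 at 90% power (two-sided P value 0.05) would require 244 patients".
- Attrition is introduced with the words "there is a risk of loss to follow-up (other than death"), and the range given for most previous trials is 10% to 30%. The first inflation used 20% and gave 305.
- In May 2024 primary-outcome completion was 75% and deaths during follow-up were 12/182 (7%). The stated aim of the increase was to "ensure complete follow-up for at least 244 surviving patients". Loss was then taken, as a conservative figure, to be as high as 30%.
- Result: "This required an inflation in sample size from 305 to 346 patients to ensure at least 90% power" for a 5-point difference. Section 4.1: "The total sample size is 346, allocated 1:1 between the two randomised groups".

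Section 9.2 adds the expectation that "around 20-30% of those randomised will have some missing data on the primary endpoint".

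Section 9.1 also expects covariate adjustment to increase power, without assuming a size for the gain.

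**The concern.** Section 9.1 makes two promises, a minimum number of surviving completers and a minimum power, and ties both to 346. Only one 30% factor is needed to get there. No separate allowance for death appears, although the section defines loss as excluding death, quotes a death rate and counts the target in survivors.

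There are two separate questions. Does a single 30% reduction of 346 leave 244? And are deaths inside or outside that 30%? The answers decide how many 90-day PCS values the trial should expect and what power it may quote. A reader of a null result would otherwise credit the trial with a planning figure that its own inputs may not support. Section 9.2 gives an expected missing-data fraction, and it should agree with whatever 9.1 means.

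**Working it through.** **Inputs (section 9.1):** difference 5, SD 12, two-sided 0.05, power 90%, 1:1 allocation, loss 20% then 30%, deaths 12/182 = 6.6%, completion 75%.

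**1. Reproduce the base.** Total = 4 × (1.960 + 1.282)² × 12² / 5² = 242.09, or 121.05 per arm, rounded up to 122 per arm = 244. The t-test calculation also gives 122 per arm. The stated 244 is confirmed.

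**2. Reproduce the two inflations.**
- 244 / 0.80 = 305, exactly as stated.
- 244 / 0.70 = 348.6, so 349, not 346.
- 242.09 / 0.70 = 345.8, so 346.

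The figure 346 therefore matches the unrounded base of 242.09, whereas 305 matches the rounded base of 244.

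**3. Completers and power from 346.** Power is for SD 12 and difference 5, unadjusted.

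| Reading of the 30% | Expected completers | Power, t-test | Power, normal | Randomised needed for 244 |
|---|---|---|---|---|
| Share of all randomised, deaths included | 346 × 0.70 = 242 | 89.8% | 90.0% | 349 |
| Share of survivors, deaths extra | 346 × (170/182) × 0.70 = 226 | 87.7% | 88.0% | 374 |
| Share of all randomised, deaths added | 346 × (1 − 0.30 − 0.066) = 219 | 86.7% | 87.0% | 385 |

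For comparison, 244 completers give 90.0% (t-test) or 90.2% (normal). The last column is 244/0.70 = 348.6, 244/(0.70 × 170/182) = 373.2 and 244/(0.70 − 0.066) = 384.8, each rounded up.

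Rows two and three treat all 12 deaths as falling by day 90. The text says only that they occurred during follow-up, which runs to 180 days. If some came later, the shortfall in these rows is smaller.

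**4. Total without a 90-day PCS, set against section 9.2.**
- Deaths inside the 30%: at most 30%, which fits the 20–30% of those randomised in 9.2.
- Deaths outside: 1 − 0.70 × 170/182 = 34.6%, or 30% + 6.6% = 36.6% if added. Neither fits.

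**5. What the observed 75% implies.** The denominator is not given.
- If it is survivors, total attrition so far is 1 − 0.75 × 170/182 = 29.9%.
- If it is all randomised, total attrition so far is 25%.

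**6. Covariate adjustment.** To offset the smaller number, covariates would have to explain about 1 − 226/244 = 7% of PCS variance, or 1 − 219/244 = 10% in the additive case. The protocol gives no such value, so these are required amounts, not predictions. Adjustment recovers power; it does not recover completers.

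**The case against.** A reader might infer that the sponsor forgot the deaths, and that the trial therefore has 87–88% power and a type II error of 12–13%. The documents do not establish this. The exclusion of death is stated once, where results of earlier trials are described. The May 2024 paragraph starts afresh from this trial's own completion and deaths. If the 75% is a share of survivors, combining it with 12/182 deaths gives 29.9% total attrition, almost exactly the 30% chosen. If it is a share of all randomised, deaths are already in the 25% and the 30% leaves a margin. Section 9.2, which speaks of those randomised, points the same way. On that reading power is 90% to within rounding, and 9.2 is right as it stands.

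That argument is sound as far as it goes, and it rules out treating the omission as fact. It does not remove the point. The all-cause reading departs from the only definition of loss in 9.1, and it still gives 242 rather than 244. If the 75% is of survivors, a 30% all-cause allowance equals what had already been seen, so it is not conservative.

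It is also fair that the gap is small beside other uncertainty. Section 9.1 allows an SD of 10 to 15; at 242 completers, power is about 97% at SD 10 and about 73–74% at SD 15. Covariate adjustment could plausibly recover 2 to 3 points. Both facts bear on severity, not on whether the stated figures are correct.

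**Conclusion.** The point holds, at minor to moderate severity.

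On every reading of the 30%, 346 does not give 244 surviving completers. The shortfall is 2 if deaths are included, about 18 if the 30% applies to survivors, and about 25 if the two shares are added. At least 90% power is met to rounding on the first reading (89.8% or 90.0%, by method) and not met without adjustment on the others (about 88% and 87%). The difference in power is thus 0 to 3 points.

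The firm findings are the 242 against 244, and the mismatch between a definition of loss that excludes death and arithmetic with no term for death. Which power figure applies is open, because the protocol does not give the denominators of the 75% and the 30%. The lower figures also assume that all 12 deaths fall within 90 days. Section 9.2 conflicts with 9.1 only if the 30% excludes deaths.

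**What to change.** In section 9.1:

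1. State whether the 75% completion and the 30% loss are shares of all randomised or of survivors, and whether deaths are inside the 30%. State also how many of the 12 deaths were within 90 days.
2. Replace the two guarantees with the matching expectation. If deaths are inside: 346 randomised, about 242 surviving completers, about 90% power. If deaths are outside and the 30% applies to survivors: about 226 surviving completers and about 88% unadjusted power, adding that any return to 90% would rely on covariate adjustment.

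In section 9.2, leave the 20–30% unchanged if deaths are inside the 30%. If they are not, raise the upper end to about 35–37%.

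The cost is a few sentences of protocol text. No extra patients, and no change to the design or analysis, are needed. At worst the quoted power falls by 2 to 3 points.

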9.2 PROPOSED ANALYSES

All details of the statistical approaches will be specified in a comprehensive Statistical Analysis Plan (SAP), authored by the study statistician and approved by the independent oversight committees (TSC and DMC).

General considerations: will use the Intention-To-Treat (ITT) principle for all outcomes, to estimate treatment effectiveness. However, safety data will be analysed according to treatment actually received instead of treatment allocated.

Principle analysis of PCS SF-36 score: The primary endpoint (change from baseline PCS SF-36 score) at 90 days post randomisation will be compared between randomised groups using a mixed effects linear model, with site as a random effect, and adjustment for any strongly prognostic baseline parameters (which may include age, comorbidity score, pre-ICU recalled HRQoL, length of ICU stay, ICU mobility scale, and baseline inflammation (assessed by CRP concentration)). The expectation is that around 20-30% of those randomised will have some missing data on the primary endpoint. We will address these missing data using an appropriate model for the missing data-generating mechanisms and conduct sensitivity type analyses to investigate the robustness of the findings to the assumptions behind this model.

In addition to the full ITT approach for the primary endpoint, (i.e. the real-world effect of the intervention amongst all those offered the intervention) we will also estimate the treatment efficacy (the idealised effect achieved by those fully compliant with their randomised treatment and all aspects of the protocol).

Moderation analyses of PCS SF-36 Score: We will conduct pre-specified moderation analyses on the primary endpoint. These moderation analyses will fit interaction terms for the baseline parameters and treatment group. There are 4 baseline potential moderators of interest – (a) Co-morbidity score (0-18; functional comorbidity index; a count of morbidities); (b) Recalled SF-36 score pre ICU admission; (c) ICU mobility scale (ordinal scale); and (d) Baseline level of systemic inflammation (CRP concentration; continuous measure ranging upwards from zero with normal values being <5mg/L). These analyses will explore how important these baseline parameters are in moderating how effective the intervention is for the main outcomes. We will first explore the nature of the potential interaction by fitting each baseline parameter as a continuous interaction with treatment, and if warranted, look at suitable categorisation (e.g. above vs. below the median) for ease of clinical interpretation.

Mediation analysis of PCS SF-36 score: We are also interested in understanding the mechanisms behind any treatment effect. To this end, in the main trial analysis we will conduct mediation analyses on the model described under "Principal analysis of PCS SF-36 score." The first mediation analysis will examine the role of haemoglobin concentration (anaemia severity) using blood measurements taken at baseline and 30 days post-randomisation, to determine whether this mediates the intervention's effect. Specifically, we want to assess whether the degree of anaemia correction at

30 days, according to group allocation, relates to the endpoint. The second mediation analysis will focus on systemic inflammation. Here, we will explore whether persistent inflammation mediates the impact of the number of blood transfusions on the endpoint. We will consider other potential mediators, and include these in the final SAP prior to locking the trial database.

We also plan to measure a range of biomarkers that may provide information about the mechanisms that the intervention influences the primary outcome, based on blood sampling at baseline and 30 days. These will include effects of the intervention on iron status, marrow erythrogenesis (red blood cell production), inflammation, and immune suppression. These exploratory analyses will be underpinned by a Directed Acyclic Graph (DAG) and pre-specified analysis plan.

Secondary outcomes: Secondary outcomes will be analysed using models appropriate for the type of outcome (e.g. for continuous outcomes as per the primary endpoint/principal analysis; mortality using a Cox proportional hazards model, binary outcomes with adjusted logistic regressions).

9.2.1 Health Economic Evaluation:

The cost-effectiveness of the intervention compared with 'usual care' will take the format of a within-trial cost-effectiveness analysis and use a cost-utility analysis framework. The primary health economic outcome measure will be the incremental cost per QALY at 180 days, and a further analysis will assess the cost per LYR at 180 days. In addition, the impact of the intervention on the downstream costs, health outcomes and cost effectiveness will we assessed over a 5-year time period (depending on the results of the shorter term trial main outcome analyses). The perspective for analysis will be that of the NHS budget holder, with a secondary analysis taking a wider societal perspective (e.g. including indirect costs in terms of the costs of lost productivity).

Estimation of health service costs will rely on a combination of scrutinisation of medical records by the research team, patient completed questionnaires and linkage to routinely collected administrative healthcare data (the decision on the latter approach will be determined based on the results of the main trial and any effects seen). This will include Hospital Episode Statistics (HES) in England and the Scottish Morbidity Record (SMR), Patient Level Costing and Information System (PLICS), the Prescribing Information System (PIS) and the Unscheduled care DataMart in Scotland to include, inpatient, outpatient, A&E, community prescribing and unscheduled care. This efficient strategy will limit missing data and accurately reflect real-world activity. Unit costs for all resources used will be obtained from routine published UK/national sources (e.g. NHS Reference Costs, the Personal Social Services Research Unit).

Assessment of quality of life (health-related utility) for the estimation of QALYs will rely on the SF-6D derived from the SF36. Longitudinal utility will be adjusted for baseline values.

To summarise the analysis will present the Incremental Cost-effectiveness Ratio (ICER), the Scatterplot on the Cost-effectiveness Plane and the Cost-effectiveness Acceptability Curve (to show the probability that the intervention is cost-effective for different values of willingness to pay per additional QALY). Moderation analysis will

reflect the main statistical analysis and multivariable analysis of cost outcomes will rely on generalised linear models. Uncertainty will be estimated using non-parametric bootstrapping (for calculating the confidence intervals around cost per QALY ratios, using bootstrapped estimates of the mean cost and QALY differences). Missing data will be handled as considered most appropriate at the time of analysis, likely using multiple imputation.

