- 6. Consent provided (by participant or in accordance with appropriate mental capacity legislation for the site)

Exclusion criteria

- 1. Contraindication or objection to RBC transfusion
- 2. Active bleeding when screened
- 3. Primary neurological ICU admission diagnosis, including primary brain or spinal cord injury
- 4. Patients discharged from the ICU following cardiac surgery
- 5. Currently receiving or planned to receive end-of-life care
- 6. Not expected by clinical team to survive to hospital discharge.
- 7. Patient with a proven chronic haematological disease that requires regular RBC transfusion to treat anaemia
- 8. Patient with dialysis-dependent chronic renal failure prior to ICU admission
- 9. Patient receiving regular erthyropoietin (or any erythropoiesis stimulating agent) treatment for anaemia prior to ICU admission.
- 10. Unable to obtain consent (from patient or in accordance with appropriate mental capacity legislation for the site)
- 11. Readmission to ICU during current hospitalisation episode and not enrolled following previous ICU admissions
- 12. Patient recovering following liver transplantation, kidney transplantation, or combined kidney/pancreas transplantation
- 13. Patient recovering from variceal bleeding due to chronic liver disease
- 14. Prisoners
- 15. Patient due for imminent hospital discharge within the next 24 hours

RANDOMISATION: Allocation 1:1 by remote computer randomisation (stratified by centre in blocks).

TREATMENT GROUPS:

Intervention group: All patients will receive a single unit RBC transfusion post-randomisation. Single RBC transfusions will subsequently be administered to achieve and maintain Hb 100-120g/L until hospital discharge. Hb measured at least weekly in hospital. Hb transfusion trigger <100g/L

Comparator 'usual care' group: Current usual care transfusion practice, namely single RBC transfusions when Hb less than 70g/L (or modified according to clinician decision) to achieve target Hb 70-90g/L. Hb measured at least weekly in hospital.

Co-interventions: all other aspects of care will be according to clinician decisions. Other treatments for anaemia, such as iron therapy, will be permitted in both groups but decided by treating clinicians.

Duration of intervention: From randomisation until acute hospital discharge (typically 2-3 weeks).

OUTCOMES:

Primary outcome: Physical Component Score (PCS) of the SF-36 HRQoL questionnaire at 90 days post-randomisation.

Secondary outcomes:

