2.3.2 Secondary Endpoints/Outcomes

Patient centred outcomes:

- 1. Physical Component Score (PCS) of the SF-36 HRQoL questionnaire (and its four sub-domains) at 30 and 90 days post-randomisation.
- 2. Patient fatigue (Fatigue Severity Scale (FSS)) at 30, 90 and 180 days post-randomisation
- 3. Mental component score SF-36 (and its four sub-domains) at 30, 90 and 180 days post-randomisation.
- 4. Activities of Daily Living (ADLs) (WHODAS questionnaire⁴) at 90 days post-randomisation
- 5. Patients alive at 30, 90 and 180 days post-randomisation
- 6. Patients alive at 5 years post-randomisation derived from data linkage
- 7. Haemoglobin concentration at 30 days post-randomisation

Resource use and cost-effectiveness (based on data linkage and questionnaires):

- 8. Post-ICU length of hospital stay;
- 9. Care costs during 180 days post-randomisation.

- 10. Incremental cost per QALY at 180 days
- 11. Care costs derived from data linkage during 5 years post-randomisation (depending on results from shorter term outcome analysis)

Process and Safety outcomes:

- 12. Protocol compliance (during intervention index hospital stay)
- 13. Hb concentration (during index hospital stay)
- 14. RBC use (during 90 days follow up)
- 15. New Infections (during 90 days follow-up)
- 16. Transfusion-related adverse events (during 90 days follow-up)
- 17. Major adverse cardiovascular events (MACE; during 90 days follow-up)

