3.3 RESEARCH QUESTIONS

3.3.1 'PICO' research guestion:

Population: ICU survivors with moderate-severe anaemia (WHO definition; Hb≤94g/L). Intervention: RBC transfusion practice to maintain Hb at 100-120g/L during subsequent hospital stay; transfusion trigger <100g/L

Comparator: Current usual RBC transfusion practice to maintain Hb 70-90g/L; transfusion trigger <70g/L

Primary Outcome: Physical Component Score (PCS) of the SF-36 HRQoL questionnaire 90 days post-randomisation

Secondary Outcomes:

To determine whether the intervention improves: Patient fatigue; Patient disability (function and activities of daily living (ADLs)); Rates of major adverse cardiac events (MACE); Survival (up to 5 years); Health service resource use and costs (up to 5 years – according to results of the shorter term outcomes).

To evaluate if the intervention is cost-effective.

3.3.2 Personalised medicine questions:

To explore whether any of the following modify the efficacy of the intervention:

Prediction variables (moderation analyses) – baseline predictive factors

- 1. Pre-existing HRQoL
- 2. Pre-existing co-morbidities
- 3. Mobility status at ICU discharge
- 4. Baseline severity of inflammation (based on C Reactive Protein concentration)

Mechanistic factors (mediation analyses) – post ICU causal mediating factors:

- 5. Persisting systemic inflammation
- 6. Evidence of impaired erythrogenesis

3.3.3 Cost effectiveness questions:

We will estimate cost per life-year and cost per Quality-Adjusted Life Year (QALY) over the follow-up period of the study. Health service costs will rely on patient questionnaires. Depending on the results of the short-term outcomes, linkage of routinely collected healthcare data, including inpatient, outpatient, A&E, and unscheduled care may be undertaken.

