5.2.3 Withdrawal of Study Participants

There will be no pre-defined participant withdrawal criteria based on medical criteria. Participants are free to withdraw from the study at any point or a participant can be withdrawn by the Investigator if this is considered clinically appropriate. In the case of incapacity, the representative of the participant can also withdraw the patient from the trial.

It is recognised that responsible clinicians may decide to suspend group allocation in certain circumstances based on their clinical judgement. Examples may include bleeding events, acute cardiovascular events, or other periods of clinical deterioration. In this situation, the patient should not be withdrawn from the trial unless the clinician specifically requests this. Ideally, the patient should be re-established on group allocation after the acute situation has resolved. Wherever possible the patient should remain in the trial for follow-up even if a decision is made to permanently suspend group allocation (see option 1 below).

If withdrawal occurs, the participant will have the following withdrawal options:

- 1. From any further study intervention only (ie the two transfusion groups). Further blood transfusions at the discretion of the clinical team. However, all follow up data collection (including the visit at 30 days if appropriate) will be completed as far as possible. The priority in this situation is the completion of the primary outcome (SF-36 PCS at 90 days).
- 2. From any further study intervention and data collection. All data collected until the point of withdrawal can be retained. In this situation, effort should be made to request that the primary outcome data at 90 days (SF-36 PCS) can be collected even if other

follow up is not completed. If the participant agrees, then this is re-classified as 'option 1' but restricted to primary outcome.

3. From all aspects of the trial and follow up. All research data collected to be removed from analysis.

If withdrawal occurs, the primary reason for withdrawal will be documented in the participant's case report form, if possible. The type of follow-up (if any) will be documented in the case report form.

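### Comparing MACE and new infections by an undefined treatment received, instead of by allocation, gives up randomisation for the safety objective

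*Protocol*

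**What the plan says.** The general considerations in section 9.2 state that the trial "will use the Intention-To-Treat (ITT) principle for all outcomes, to estimate treatment effectiveness". The next sentence makes an exception: "safety data will be analysed according to treatment actually received instead of treatment allocated". The protocol does not say whether treatment received means any transfusion, a number of units, or which strategy was followed.

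The process and safety outcomes in section 2.3.2 include "New Infections (during 90 days follow-up" and "Major adverse cardiovascular events (MACE; during 90 days follow-up", together with transfusion-related adverse events. Section 3.3.1 puts "Rates of major adverse cardiac events (MACE" among the outcomes that the intervention may improve. One secondary objective in section 2.2 is the safety of correcting anaemia compared with current usual care.

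Usual care is itself a transfusion strategy. The Summary describes it as "single RBC transfusions when Hb less than 70g/L (or modified according to clinician decision". Section 6.1.2.2 lets the responsible clinician change the threshold for the patient's condition, and directs the restrictive threshold at patients without major haemorrhage or acute coronary syndrome. Section 5.2.3 lets clinicians suspend the allocation in either arm: "Examples may include bleeding events, acute cardiovascular events, or other periods of clinical deterioration".

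**The concern.** An as-treated safety set suits a trial in which a patient either gets a drug or does not, and this is mostly settled at the start. Here exposure builds up after randomisation and follows the patient's course.

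- **Confounding by indication.** Usual-care patients who are transfused, or whose allocation is suspended, may be sicker than the rest. Regrouping on that basis compares patients with different prognoses.
- **Reverse causation, for MACE.** Myocardial infarction is a component of MACE (section 7.3, Table 1). An infarction can take a usual-care patient off the restrictive threshold and lead to a transfusion. The event is then counted against transfusion although it came first.
- **Wrong question.** The objective in section 2.2 compares strategies. A usual-care patient transfused below 70 g/L has received the allocated strategy.
- **Two MACE results.** As an effectiveness outcome MACE falls under intention to treat, and as a safety outcome under treatment received. No rule says which result prevails.

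What is at stake is a harm signal, or a reassuring result, produced by selection in a trial whose purpose is to weigh the benefits of transfusion against its risks.

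**Working it through.** **Inputs.** The protocol gives no figure for the safety comparison, so there is none to reproduce. Section 4.1 gives 346 patients allocated 1:1, which is 173 per arm. The only event count is deaths, 12/182 = 6.6% (section 9.1). There is no crossover, infection or MACE rate. All rates below are assumptions, and every case has **no true effect**, so the risk ratio (RR) by allocation is 1.00.

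**Reading A: received means ever transfused.** A share *f* of each arm is high-risk (event risk *r1*) and the rest have risk *r0*. All high-risk usual-care patients are transfused and no others. A share *z* = 5% of the liberal arm, all low-risk, is never transfused.

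Risk if transfused = [2*f*·*r1* + (1 − *f* − *z*)·*r0*] / (1 − *z* + *f*). Risk if not transfused = *r0*.

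| *f* | *r1* / *r0* | Transfused | Not transfused | RR |
|---|---|---|---|---|
| 0.10 | 0.30 / 0.15 | (0.060 + 0.1275)/1.05 = 0.179 | 0.150 | 1.19 |
| 0.20 | 0.30 / 0.15 | (0.120 + 0.1125)/1.15 = 0.202 | 0.150 | 1.35 |
| 0.20 | 0.45 / 0.15 | (0.180 + 0.1125)/1.15 = 0.254 | 0.150 | 1.70 |

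These cases are severe, because every transfused usual-care patient is high-risk. A haemoglobin below 70 g/L can trigger transfusion without deterioration. So let 20% of usual care be transfused with only half of them high-risk, keeping 20% high-risk per arm (0.30 v 0.15):

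- transfused: (0.1725 + 0.045)/1.15 = 0.189
- not transfused: (0.135 + 0.0075)/0.85 = 0.168
- RR = 1.13

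**Second parameterisation of A.** Let the overall event risk be *p*, let a share *c* of usual care be transfused at *k* times the risk of other usual-care patients, and let all liberal patients be transfused. Risk in the untransfused is *p*/(1 − *c* + *ck*).

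- *p* = 0.15, *c* = 0.2, *k* = 2: untransfused 0.15/1.2 = 0.125; transfused (0.15 + 0.2 × 0.25)/1.2 = 0.167; RR 1.33. A pooled z-test at two-sided 0.05 would reject in 18% of trials instead of 5%.
- *c* = 0.1, *k* = 2: RR 1.18, with rejection in 7%, 10% and 14% of trials at *p* = 6.6%, 15% and 25%.
- *c* = 0.3, *k* = 3: RR 1.92, with rejection in 26%, 58% and 86%.
- *k* = 1: RR 1.00 and rejection in 5%. With equal risks there is no bias.

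**Reading B: received means strategy followed.** Usual-care transfusions within the rules move nobody. Each arm has risk 0.2 × 0.30 + 0.8 × 0.15 = 0.18.

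- 5% of usual care, all high-risk, counted as liberal: (0.18 + 0.015)/1.05 = 0.186 against (0.18 − 0.015)/0.95 = 0.174; RR 1.07.
- An equal high-risk 5% also moving the other way: RR 1.00.
- Only the liberal arm losing such patients: the mirror image, 0.174/0.186 = 0.94.

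**The case against.** Much can be said for the plan, and several stronger readings fail.

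- **Sickest usual-care patients become the transfused group.** A reader might infer that the rule does this and so manufactures harm. That needs the ever-transfused reading, which the protocol does not fix. Sections 6.1.2.2 and 6.1.3 treat a usual-care transfusion below 70 g/L, or at a higher value with a stated reason, as within usual care. If received means strategy followed, such patients stay put. Suspension under section 5.2.3 applies to both arms, so the direction is open too. This objection stands, and it limits the claim to a risk of bias.
- **Section 9.2 contradicts itself.** A reader might infer this from intention to treat for all outcomes. The wording ties that principle to effectiveness and introduces safety as an exception, so it is deliberate. What remains is the double role of MACE.
- **Mortality is affected.** Survival is a patient-centred outcome in section 2.3.2 with a Cox model in section 9.2, so it falls under intention to treat.
- **The triggers for transfusion are themselves the safety outcomes.** Only acute cardiovascular events clearly overlap. Bleeding and general deterioration are not listed safety outcomes, and infection is not named as a reason to transfuse or suspend.
- **Exposure-based reporting is legitimate for transfusion reactions.** This stands.
- **The analysis plan may define treatment received.** It may, but the choice to replace allocation is made in the protocol. A definition would not restore the randomised comparison.

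**Conclusion.** The concern holds as a stated rule that does not suit this design, for two outcomes: MACE and new infections. The path from outcome to exposure is documented for MACE. For infections the case rests on confounding by condition alone.

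The size cannot be derived from the protocol. With no true effect, the assumed cases give 1.00 when transfused usual-care patients carry the same risk as the rest or when moves between strategies balance. They give about 1.1 to 1.35 in moderate cases and 1.7 or more in extreme ones. The larger figures need the ever-transfused reading and strong selection, and they are not predictions. Comparison by allocation gives 1.00 throughout.

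The primary endpoint, the other effectiveness outcomes and survival are untouched. This is a should-fix.

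**What to change.** Replace the safety sentence in section 9.2 with a rule to this effect: *MACE and new infections will be compared primarily by allocated group in all randomised patients. Transfusion-related adverse events will be reported by allocated group and also per transfused patient or per unit transfused. Any other as-treated safety table will be supplementary and descriptive.* Define treatment received for those tables, and the timing of each event relative to transfusion. Survival needs no change. The single rule for MACE also removes its double role.

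The cost is one amended passage, carried into the analysis plan. No extra patients are needed. Section 7.3 already records transfusion dates during the intervention, but event dates would have to be available for the timing rule. The downside is that safety is no longer tabulated primarily by exposure; the per-patient or per-unit table keeps that information where it is most useful.
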